The primary aim of the study is to determine the effects of beta-glucan, a dietary fiber supplement isolated from baker's yeast, on immune response to the influenza vaccine.

Primary outcome

• Change in immune response to the influenza vaccine after beta-glucan supplementation [Time Frame: 28 days (Baseline (day 1), pre-vaccine visit (~day 1), and study end (~day 28)]; Influenza-specific antibodies (IgM, IgG influenza A and B).

Secondary outcomes

- Inflammatory cytokine profile (TNF-α, IL-1β, IL-6, IL-8, and IFN-γ) [Time Frame: 28 days (Pre-vaccine visit, post-vaccine visit (~day 2-3) and study end)]
- Self-reported incidence of influenza and COVID-19 (Note: Data of subjects reporting incidence of influenza or COVID-19 during the study will be excluded from the final analysis) [Time Frame: 28 days]
- Number of subjects with fever during the study [Time Frame: 28 days] Body temperature (°C)
- Number of subjects with cold and flu symptoms [Time Frame: 28 days] Modified Jackson Criteria
- Fatigue [Time Frame: 28 days (Days 1 28)

Additional information collected

- Demographic data
- Adverse events
- Vaccinations (including COVID-19 booster) received during the month prior to the study start and during the study period
- Compliance

- o Reported intake of the supplement.
- Number of unconsumed supplements (returned)

Study Participants

This is a 2-arm placebo, controlled study. A total of 120 volunteers (60 in each arm) will be recruited for the study. Subjects who do not meet the inclusion criteria or who meet any of the exclusion criteria will not be eligible to participate.

Sample Size Calculation

This is a pilot study, and thus sample size is based on similar published studies.

Inclusion criteria

- 1. Adult volunteers \geq 40 years of age.
- 2. Planning to be vaccinated for influenza
- 3. Have been immunized for COVID-19 (self-disclosure)
- 4. Willing and able to provide written informed consent in English.
- 5. Willing and able to comply with all the study-related procedures, including attending to study visits for blood draw, taking the influenza vaccine, intake of the study supplement, and completing study questionnaires.

Exclusion Criteria

- 1. Demonstrate an inability to comply with the study-related procedures.
- 2. Have a history of a severe reaction or hypersensitivity following vaccination with influenza vaccine, vaccination with any other vaccine containing the same substances, or intake of the study product.

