The product under study is beta-glucan at 500 mg/day (2 capsules per day). The group randomized to the beta-glucan intervention will receive sufficient IP to cover the entire length of the intervention period (28 days).

Placebo

The placebo product is cellulose, an inert dietary fiber, 500 mg/day (2 capsules per day). The product has a very similar appearance, texture and taste as the beta-glucan product and will have identical packaging. The group randomized to the placebo intervention will receive sufficient IP to cover the entire length of the intervention period (28 days).

Direction of Use

Participants will be instructed to consume the supplement (500 mg/d) for 28 days following the influenza vaccination.

Study design

This is a 6-week randomized, double-blind, placebo-controlled, 2-arm parallel study designed to evaluate the adjuvant effect of beta-glucan dietary supplementation during influenza vaccination. This study will have a 28-day intervention period.

During the pre-screening by telephone or in-person, the study and inclusion and exclusion criteria will be explained. Any restrictions linked to the study will also be explained. Sufficient time will be allowed for the potential participants to decide whether or not they wish to participate in the clinical study. If the potential participant decides to participate, a screening appointment will be scheduled to sign the informed consent and to perform the first study activities.

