Statistical consultation will be utilized for data analyses. Statistical methods will be consistent with the CONSORT 2010 Statement (including statistical methods used to compare groups for primary and secondary outcomes and methods for additional analyses, such as subgroup analyses and adjusted analyses).

Data Management Plan

Data about the intervention effects will be collected from the participants electronically and on paper. Data and files will be secured in locked filling cabinets and office space. Paper questionnaires will only include date and research study assigned participant number. Data that is originally captured as hardcopy/paper (e.g., demographics and vital signs) will be transcribed to encrypted electronic files.

Following the completion of the study, identifiers will be removed from data to meet HIPAA deidentification standards (According to the October 2002 Privacy Rule § 164.514.(b).2. the indicated information/will be removed from all study records).

All software applications used in the collection of data will be properly validated following standard computer system validation that is compliant with all regulatory requirements.

Potential Discomforts and Risks

Beta-glucan, a dietary fiber, poses no known risks. Beta-glucan, a fiber, poses no known risks. However, there are some potential discomforts and risks related to the study. Drawing blood from a vein may result in discomfort at the site of puncture; possible bruising and swelling around the puncture site; rarely an infection; and, uncommonly, faintness from the procedure. Some people may feel uncomfortable answering questions about incidence of influenza, cold and flu symptoms, mood and feelings, and fatigue symptoms. Some people may feel uncomfortable or have difficulties swallowing capsules. You can open the capsule and add to a food such as apple sauce if you prefer. There is a risk of possible loss of confidentiality.

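### For the supplement, exclusion 2 covers only a past reaction to taking the study product, so a volunteer with a known yeast or capsule-ingredient allergy who has never taken it is eligible as written

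*Combined protocol and SAP*

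**What the plan says.** Item 2 of the Exclusion Criteria has three parts. The first is "Have a history of a severe reaction or hypersensitivity following vaccination with influenza vaccine". The second and third continue the same sentence: "vaccination with any other vaccine containing the same substances, or intake of the study product".

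The opening statement of the aim describes the active product as "beta-glucan, a dietary fiber supplement isolated from baker's yeast". The Investigational Product section gives its form, "The product under study is beta-glucan at 500 mg/day (2 capsules per day", and that of the comparator, "The placebo product is cellulose, an inert dietary fiber, 500 mg/day (2 capsules per day". It lists no shell material or other ingredient for either capsule.

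The Study Participants section makes the listed criteria decisive: "Subjects who do not meet the inclusion criteria or who meet any of the exclusion criteria will not be eligible to participate". Potential Discomforts and Risks says "Beta-glucan, a dietary fiber, poses no known risks". It mentions difficulty in swallowing capsules but not allergy.

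**The concern.** The criterion treats its two exposures unequally. For vaccines it looks through to the constituents, so a reaction to a different vaccine that shares a substance is enough to exclude. For the supplement it asks only about a past reaction to the product itself. Many volunteers may never have taken a yeast beta-glucan supplement and would have no such history to report, whatever they know about their own allergies.

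The wording matters more here than in a trial with a clinical work-up at entry, because the screening that the protocol describes rests on the volunteer's own answers to the listed items. An allergy that no item asks about may not come up. What is at stake is the safety of perhaps one person and the adequacy of a stated safety rule. The trial's estimates are not threatened.

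**Working it through.** The protocol gives no figure to reproduce. The check is mainly a reading of the text, followed by a short calculation on an assumed rate.

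**Step 1: what item 2 covers.**

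| Exposure | Past reaction to the item itself | Past reaction to something sharing its substances |
|---|---|---|
| Influenza vaccine | Excluded | Excluded (other vaccines with the same substances) |
| Study supplement | Excluded | Not mentioned |

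The phrase about shared substances is attached to other vaccines. Grammatically it does not carry over to the supplement.

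**Step 2: whether another criterion closes the gap.**
- Exclusion 1 concerns inability to comply with procedures.
- Exclusion 3 concerns immune-suppressing treatment.
- Exclusion 4 concerns concurrent trials. The only investigator judgement in the list is here, and it is limited to interference from another trial.
- Inclusion 5 requires the volunteer to be willing and able to follow procedures, including taking the supplement.

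None of these mentions allergy, and none gives a general discretion to exclude on safety grounds.

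**Step 3: whether the screening process described would bring it out.** Under Recruitment, the criteria are read aloud and volunteers judge for themselves whether to go on. Under Study design, the criteria are answered and recorded item by item after consent. The only form described before Visit 1 is demographic: age, sex, race and ethnicity. The text available describes no medical or allergy history.

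**Step 4: size.** The prevalence of known yeast or capsule-ingredient allergy is not in the documents. A range of 0.1% to 1% is assumed, for illustration only. The number of beta-glucan participants, 60, is from Study Participants.

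- Expected number affected in the beta-glucan arm = 60 × prevalence: 60 × 0.001 = 0.06, and 60 × 0.01 = 0.6.
- Expected number that a wider criterion would turn away, per 120 volunteers = 120 × prevalence: 120 × 0.001 = 0.12, and 120 × 0.01 = 1.2.

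The second line uses all 120 because eligibility is settled before randomization. The first uses 60 because only that arm receives the yeast product. If both capsules share a shell ingredient, an allergy to that ingredient would concern both arms. The documents do not say whether they do.

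**The case against.** The strongest reply is that the gap is narrower than it looks and its consequences are unproven. Much of this stands.

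- **Meaning of study product.** The Investigational Product section identifies the product simply as beta-glucan. A past reaction to any yeast beta-glucan supplement may therefore already be covered. This is a fair reading. It leaves uncovered an allergy to yeast generally, or to a capsule ingredient, in someone who has never taken beta-glucan.
- **Other prompts.** The pre-screening script is not reproduced, the consent pages were removed before review, and Study design says that restrictions linked to the study will be explained. A reader might infer that nothing at screening would prompt the volunteer. The documents support only that no prompt appears in the text available. A volunteer told of the yeast source might also decline, or be judged not able to take the supplement. Such a safeguard is indirect and does not amend the criterion.
- **Seriousness.** A reader might infer a foreseeable, serious reaction. The documents do not say whether the isolate retains yeast allergens and list no capsule ingredients, so they do not support this.
- **Attribution.** A reader might infer that blinding would prevent a reaction from being separated from the same-day vaccine. Every participant is vaccinated, so opening the code would not separate capsule from vaccine in a beta-glucan participant. Capsules are taken over 28 days, so a reaction need not fall on the vaccination day. The Unblinding section already allows a code break where a serious adverse event requires it.
- **Loss from follow-up.** A reader might infer that someone who stops the capsules drops out of the 28-day outcomes. The Compliance section only labels intake below 80% as noncompliant. Nothing there cancels Visit 3.
- **Cellulose.** The protocol calls it inert, and nothing in the documents supports a concern about allergy to it.

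**Conclusion.** The point holds as a gap in the wording of one eligibility rule. As written, item 2 does not exclude a volunteer with a known yeast or capsule-ingredient allergy who has never taken the product, and no other listed criterion does so. This sits poorly with the protocol's own statement that the product comes from baker's yeast.

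The expected number affected is below one: about 0.06 to 0.6 of 60, resting wholly on the assumed 0.1% to 1% and taken before any self-exclusion. The clinical risk to such a person cannot be judged from the documents. There is no effect on power, estimates or interpretation. The change is worth making because it makes a stated safety rule consistent at almost no cost, and because that rule works by self-report.

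**What to change.** Reconcile the supplement part of exclusion 2 with the stated yeast source and capsule form, so that it covers known hypersensitivity to the product's source or ingredients, as the vaccine part already does for shared substances. The sponsor knows the full composition of both capsules and should set the exact ingredient wording. The same line should go into the pre-screening script and into the criteria recorded item by item after consent. If the script or consent form already carries an allergy statement, the criterion should be brought into line with it.

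The cost is one phrase in one criterion and in the script. At the assumed prevalence, at most one or two of 120 volunteers would no longer be eligible.

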During the screening appointment (by Zoom or in person), the inclusion and exclusion criteria will be reviewed without responses to the individual items, and if the participant believes they are qualified, the informed consent will be signed via RedCap or in person. Following informed consent, the inclusion and exclusion criteria will be reviewed again, this time with responses to each item and recorded. Each study participant will receive a unique identifier. Within 24-hr prior to Visit 1, links to the Qualtrics demographic form (age, sex, race, and ethnicity) will be sent to participants for completion. Alternatively, the participant will be given the option of completing the questionnaire in person during Visit 1. At Visit 1, a baseline blood draw will be performed, and the participants will be randomized to either the beta-glucan or placebo group and will be instructed about the daily consumption of the IP for 28 days. Participants will then receive an influenza vaccine. Take-away breakfasts will be offered following blood draws. Participants will be requested to complete an online Qualtrics or paper-based daily questionnaire of compliance, and cold, and flu and fatigue symptoms throughout the 28-day study.

A second blood draw within 24-48 hours following their influenza vaccination (Visit 2) will be taken. A final blood draw will be completed on day 28 (Visit 3 - study end). Adverse events, including any illnesses, will be queried.

Randomization

Participants will be randomized to either the beta-glucan or the placebo group in a 1:1 fashion. Randomization will be used in this study to avoid bias in the assignment of participants to intervention, to increase the likelihood that known and unknown participant attributes (e.g., demographics and baseline characteristics) are balanced across intervention groups, and to ensure the validity of statistical comparisons across intervention groups.

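### No fatigue or cold/flu symptom reading is specified before randomisation and vaccination, and no rule separates symptoms already present at Visit 1 from new ones

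*Combined protocol and SAP*

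**What the plan says.** All references are to the combined protocol and SAP.

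- **Before Visit 1 (Study design).** Within the preceding 24 hours, "links to the Qualtrics demographic form (age, sex, race, and ethnicity) will be sent to participants for completion". Participants may instead complete this form at Visit 1.
- **Visit 1 (Study design).** "At Visit 1, a baseline blood draw will be performed, and the participants will be randomized to either the beta-glucan or placebo group". Supplement instruction is given, and then "Participants will then receive an influenza vaccine". No fatigue or symptom assessment is named at this visit.
- **Daily record (Study design).** Participants are asked for a "daily questionnaire of compliance, and cold, and flu and fatigue symptoms throughout the 28-day study". The hour of the first entry is not given.
- **Outcomes (Secondary outcomes).** Fatigue is listed as "Fatigue [Time Frame: 28 days (Days 1 28"; the separator between 1 and 28 is missing, possibly lost when the PDF was read. The symptom outcome is "Number of subjects with cold and flu symptoms [Time Frame: 28 days] Modified Jackson Criteria", with no definition of new onset.
- **Meaning of Day 1 (Primary outcome).** For the antibody outcome the time frame is "28 days (Baseline (day 1), pre-vaccine visit (~day 1), and study end (~day 28", so Day 1 carries the label of baseline there.
- **Elsewhere.** The Exclusion Criteria do not mention illness or fatigue present at Visit 1. The Data Analysis Plan names no covariate and no case definition.

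**The concern.** Fatigue is likely to vary considerably between adults aged 40 and over, whatever supplement they take. Without a score taken before allocation, the arm comparison carries all of that variation, and a chance imbalance between arms can be neither seen nor adjusted for. For the symptom count, someone who arrives at Visit 1 with a cold is not excluded by the listed criteria and may be counted as a case that the supplement had no opportunity to prevent. Such cases add equally to both arms on average and shrink the contrast.

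The Day 1 entry might fill the gap, but its timing is open. If it is made that evening, it follows the vaccine and perhaps the first capsule, and it could not tell a pre-existing symptom from a vaccine reaction. A reading not taken before allocation cannot be recovered later.

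**Working it through.** **1. Does the schedule contain an earlier reading?** Three sections bear on when the daily questionnaire starts.

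- Study design makes compliance with the supplement part of the questionnaire.
- Compliance says that the questionnaire monitors intake and adverse events during the intervention phase.
- Direction of Use places the 28 days of supplement after the vaccine.

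Taken together, these make a start after allocation the natural reading, but none of them times the Day 1 entry.

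The plan's own payment figure can be reproduced from Compensation: 3 draws × $25 + 4 weeks × $25 = $75 + $100 = $175, as stated. Four weeks × 7 = 28 days, so no separate pre-study questionnaire week is paid for. This agrees with the reading above but does not exclude a Day 1 entry made before the envelope is opened.

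**2. Precision on fatigue.** The input from the plan is 60 per arm (Study Participants). The correlation ρ between baseline and follow-up fatigue is an assumption, since no scale or summary measure is given. Dropout is ignored.

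- Without a baseline: SE = √(2/60) = 0.183 SD.
- With a baseline covariate: SE = √(2/60) × √(1 − ρ²).
- Equivalent n per arm without a baseline: 60/(1 − ρ²).
- Detectable difference, assuming two-sided 5% and 80% power: (1.960 + 0.842) × SE.

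| Assumed ρ | SE (SD) | Equivalent n per arm | Detectable difference (SD) |
|---|---|---|---|
| no baseline | 0.183 | 60 | 0.511 |
| 0.3 | 0.174 | 66 | 0.488 |
| 0.5 | 0.158 | 80 | 0.443 |
| 0.7 | 0.130 | 118 | 0.365 |

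The sample size of 120 cannot itself be reproduced, because the plan bases it on similar published studies and gives no inputs. The point does not depend on it.

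**3. Dilution of the symptom count (illustration only).** Assume true new-onset rates of 30% and 15%. Assume also that a share q of each arm is symptomatic at Visit 1 and that all of these count as cases. The observed rates are q + (1 − q) × 0.30 and q + (1 − q) × 0.15, so the difference is (1 − q) × 15 points. Power is for a two-sided 5% comparison of two proportions (pooled variance under the null).

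| Assumed q | Observed rates | Difference (points) | Power, all counted, 60 per arm | Power, 30% v 15% among those symptom-free at Visit 1 |
|---|---|---|---|---|
| 0 | 30.0% v 15.0% | 15.0 | 50% | 50% (60 per arm) |
| 5% | 33.5% v 19.3% | 14.25 | 42% | 48% (57 per arm) |
| 10% | 37.0% v 23.5% | 13.5 | 36% | 46% (54 per arm) |
| 20% | 44.0% v 32.0% | 12.0 | 27% | 42% (48 per arm) |

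The last column takes 60 × (1 − q) per arm. A new-onset rule recovers much of the loss but not all of it, because fewer people are at risk.

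**The case against.** The strongest reply is that fatigue is listed from Day 1, and Day 1 is called baseline for the primary outcome. If the garbled time frame meant Days 1 and 28, a first and a last reading are intended; if it meant Days 1 to 28, entries still begin on Day 1. The order of sentences in Study design is not a strict timeline either: breakfast after the blood draw is mentioned after the vaccine. Nor is that narrative complete. It leaves room for unspecified activities at screening, calls the study six weeks long with a 28-day intervention, and does not schedule the vital signs mentioned in the Data Management Plan or the mood questions mentioned under Potential Discomforts and Risks.

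Much of this stands, and it rules out several stronger readings that a reader might infer:

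- *Fatigue has no baseline, or is first recorded after randomisation.* The documents do not say so. The Day 1 entry is untimed, which is a different defect.
- *Pre-existing symptoms cannot be separated from later ones.* This is too strong. Daily entries distinguish a symptom reported on Day 1 from one starting on, say, Day 10. The ambiguity lies in the first entry.
- *A fixed number of false cases, such as 6 to 12 of 120.* That needs an assumed prevalence of 5% to 10% and a rule under which any symptom qualifies. The content of the modified Jackson criteria is not given, and some of these people would become cases anyway.
- *The comparison is biased.* Randomisation protects it; the harm is lost precision and a diluted contrast.

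It is also fair that these are secondary outcomes in a declared pilot, and that at ρ = 0.3 the gain is small.

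The reply does not supply a reading specified before allocation and vaccination. The baseline label for Day 1 belongs to the antibody measurement, and Day 1 is also the day of randomisation and vaccine.

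**Conclusion.** The point holds as a gap in specification. No section places a fatigue or cold/flu reading before randomisation and vaccination, the Day 1 entry is not timed against either or against the first capsule, and no rule separates existing from new symptoms. The between-arm comparison remains valid.

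For fatigue, the cost is an SE of 0.183 SD where 0.174, 0.158 or 0.130 SD would be available, if the baseline correlation is 0.3, 0.5 or 0.7. Those correlations are assumptions, and the figures ignore dropout. For the symptom count, the direction (dilution) is clear if people symptomatic at Visit 1 are counted as cases. The size is not, because it depends on a prevalence, on event rates and on a case definition that the documents do not give. The change is worth making because it is cheap and the information cannot be collected afterwards.

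**What to change.** Under Study design:

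1. Add to the pre-visit form the same fatigue and cold/flu items that the daily questionnaire uses. State that they are completed before the randomisation envelope is opened, including when the participant fills in the form at Visit 1.
2. State when the Day 1 daily entry is made relative to the vaccine and the first capsule, so that it is not mistaken for the baseline.

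In the Data Analysis Plan:

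3. Use the baseline fatigue score as a covariate for the fatigue outcome.
4. Count cold/flu cases as symptoms not already present at that baseline.

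The fever count shares the feature that no pre-randomisation temperature is scheduled, so the sponsor could settle it in the same edit.

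The cost is a few minutes per participant on a form already being sent, plus a few sentences in the plan. Dose, eligibility and visit schedule are unaffected.
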